6.3.2 Follow-up for toxicities

All patients will be followed for adverse events and serious adverse events for 30 days following the last dose of study drug. Beyond these 30 days, any serious adverse events that are suspected to be related to the study drug will also be collected.

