10.5.3 Safety objectives

10.5.3.1 Analysis set and grouping for the analyses

For all safety analyses, the safety set will be used.

The overall observation period will be divided into three mutually exclusive segments, which all applicable listings and tables will be presented by:

1. pre-treatment period: from day of patient's informed consent to the day before first dose of study medication
2. on-treatment period: from day of first dose of study medication to 30 days after last dose of study medication
3. post-treatment period: starting at day 31 after last dose of study medication.

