5.4.2 Adverse events (AEs)

Adverse events (AEs) were coded according to the latest version of MedDRA prior to database lock.

If an outcome is missing and there is no outcome date, the outcome of that adverse event will be considered "ongoing". In the causality assessment between the investigational drug and the adverse event, if the result is missing or unknown, that AE will be assessed as "suspected to be related to the investigational drug". Other missing data will be treated as missing.

Adverse events were classified by onset time of AE relative to start time of study treatment as:

- Pre-treatment period: from day of patient's informed consent to the day before first dose of study medication;

- On-treatment period: from day of first dose of study medication to 30 days after last dose of study medication;
- Post-treatment period: starting from 30 + 1 days after last dose of study medication.

In addition to the overview of adverse events, only treatment-emergent adverse events were summarized by the number and percentage of patients with AEs. However, all AEs (including pre-treatment and post-treatment AEs) were tabulated with data indicating whether the AE occurred before or during or after the treatment period. For AE with missing dates, the available information should be used as much as possible when determining the period to which the AE belongs. If it is still impossible to distinguish, please refer to Table 1.

Table 1 Handling of missing adverse event onset date

Known date information	Missing date information	Case	Period belonging to
[None]	DDMMYYYY		Treatment period
DDMM	YYYY		Treatment period
YYYY	DDMM	If year < year of time of the first dose of the study drug	Pre-treatment
		If year \geq year of time of the first dose of the study drug and \leq year of time of the last dose of the study drug	Treatment period
		If year > year of time of the last dose of the study drug	Post-treatment
MMYYYY	Day	If year < year of time of the first dose of the study drug	Pre-treatment
		If year = year of time of the first dose of the study drug, and month < month of time of the first dose of the study drug	Pre-treatment
		If year = year of time of the first dose of the study drug and month \geq month of time of the first dose of the study drug	Treatment period
		If year > year of time of the first dose of the study drug and < year of time of the last dose of the study drug	Treatment period

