		If year = year of time of the last dose of the study drug and month \leq month of time of the last dose of the study drug + 2	Treatment period
		If year > year of time of the last dose of the study drug	Post-treatment
		If year = year of time of the last dose of the study drug and month > month of time of the last dose of the study drug + 2	Post-treatment
DDYYYY	Month	If year < year of time of the first dose of the study drug	Pre-treatment
		If year \geq year of time of the first dose of the study drug and \leq year of time of the last dose of the study drug	Treatment period

Known date information	Missing date information	Case	Period belonging to
		If year > year of time of the last dose of the study drug	Post-treatment

Note: If the end date of the adverse event is prior to the first dose, the adverse event is a pre-treatment adverse event, even if the onset date of the adverse event is missing.

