5.4.2.4 Death, SAE and other significant AE

5.4.2.4.1 Death

The number and percentage of patients who died during different time periods were summarized, and the causes of deaths during treatment were summarized:

- All deaths
- Treatment-emergent deaths, defined as deaths that occurred between the start of study treatment and within 30 days after the end of treatment
- Deaths during the follow-up period, defined as those that occurred at or after 30 + 1 days after the end of study treatment.

In addition, deaths due to AE were summarized by MedDRA SOC (in alphabetical order) and PT (in descending order of incidence).

For confirmed deaths only, the date of death is imputed with the following rules:

- If the year is missing (or all missing), it is imputed with the last known survival date + 1;
- If the month and day are missing, they are imputed with January 1st of the current year;
- If only the day is missing, it is imputed with the 1st of the current month.

The last known survival date is defined as the latest of the following dates:

- All test/examination dates including all laboratory tests, vital sign tests, imaging examinations
- Treatment dates including the date of treatment with the investigational drug, concomitant drugs, concomitant non-drugs
- Onset date of adverse event and end date of adverse event with an outcome other than death
- Date of last survival in which the subject's status is not "dead" on the Survival Follow-up page
- The study completion date on the end of study page or the withdrawal date for which the reason for the withdrawal is not "lost to follow-up" and "death"

If the imputed date of death is before the last known survival date, the imputed date is modified to the last known survival date + 1. If the imputed date of death is after the referencable date of death (date of follow-up visit in which the survival follow-up status is "dead"), the imputed date is modified to the referencable date of death - 1.

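### SAP Table 1 labels a January AE with a missing day Post-treatment after a 2–31 December last dose, although it may lie inside the 30-day on-treatment window

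*SAP*

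**What the plan says.** SAP 5.4.2 defines the period that counts as treatment-emergent: "On-treatment period: from day of first dose of study medication to 30 days after last dose of study medication". Protocol 10.5.3.1 gives the same window. Apart from the AE overview, only treatment-emergent AEs are summarised by number and percentage of patients. AEs from the other periods appear in listings (SAP 5.4.2, protocol 10.5.3.2).

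For AEs with incomplete onset dates, the SAP first asks for all available information to be used, and then says: "If it is still impossible to distinguish, please refer to Table 1". In the block where month and year are known and only the day is missing, Table 1 works as follows:

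- AE year before the first-dose year, or same year but an earlier month (the row beginning "If year = year of time of the first dose of the study drug, and month"): Pre-treatment.
- AE in the first-dose year, in the first-dose month or later: Treatment period.
- AE in a year between the first-dose and last-dose years: Treatment period.
- AE in the last-dose year, up to the last-dose month + 2: Treatment period.
- AE in the last-dose year, later than that ("and month > month of time of the last dose of the study drug + 2"): Post-treatment.
- AE in any later year ("If year > year of time of the last dose of the study drug"): Post-treatment, with no condition on the month.

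A note under the table keeps an AE that ended before first dose as pre-treatment, even if its onset date is missing.

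**The concern.** The later-year row treats the turn of the year as if it were the end of the window. For most of December it is not: a patient who stops on 20 December is on-treatment until 19 January. If that patient has an AE recorded only as January, and nothing else dates it, Table 1 places it after treatment.

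The incidences of AEs, suspected AEs, Grade 3/4 AEs and SAEs are the primary endpoint (protocol Table 3-1, SAP 2.3). A misplaced AE is still listed, but it drops out of the treatment-emergent summaries. The error can only lower the reported incidence, and whether a partly dated AE counts comes to depend on where the calendar year ends.

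**Working it through.** **Inputs.** Window: first dose to last dose + 30 days (SAP 5.4.2, protocol 10.5.3.1). Day-missing rows of Table 1 (SAP 5.4.2). About 60 patients (SAP Section 4, protocol 10.8). Assumption: every combination of last-dose day and AE day in the two months has equal weight. The plan gives no figure of its own to reproduce.

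**Step 1: which row applies.** For a December last dose and an AE in the following January, the AE year is later than both the last-dose year and the first-dose year. Every other day-missing row requires an AE year no later than one of these, so none matches. The label is Post-treatment whatever the first-dose date.

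**Step 2: where the window ends.** December has 31 days, so a last dose on December d reaches day d + 30 − 31 = d − 1 of January.

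| Last dose | Window ends |
|---|---|
| 1 December | 31 December |
| 2 December | 1 January |
| 16 December | 15 January |
| 31 December | 30 January |

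**Step 3: share of January inside the window.** For a known last dose on December d, the share is (d − 1)/31. This runs from 1/31 = 3% (2 December) to 30/31 = 97% (31 December). Over 2–31 December:

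- pairs inside: 1 + 2 + … + 30 = 30 × 31/2 = 465
- all pairs: 30 × 31 = 930
- share: 465/930 = 50%

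With 1 December included, it is 465/961 = 48%.

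**Step 4: the same arithmetic elsewhere in the table** (non-leap year).

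| Last dose – AE month | Pairs inside 30 days | Table 1 label |
|---|---|---|
| July – August | 465 of 961 (48%) | Treatment period |
| November – December | 465 of 930 (50%) | Treatment period |
| December – January | 465 of 961 (48%) | Post-treatment |
| Last-dose month + 2, January to October last doses | 3 of 9,305 | Treatment period |
| November – January | 0 of 930 | Post-treatment |
| December – February | 0 of 868 | Post-treatment |

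The later-year row is right for November–January and December–February. December–January is the only combination of these months in which an AE can be on-treatment and the table excludes it.

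**Step 5: does the case reach Table 1?** For last doses on 2–31 December, the known month and year do not settle the period, because part of January lies inside the window and part outside. Unless another recorded item settles it, the fallback decides.

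**Step 6: size.** If last doses were spread evenly over the year, 30/365 = 8% of last-dose dates would be exposed. An affected AE also needs a January onset, a missing day and no other dating information. One patient among 60 is 1/60 = 1.7 percentage points.

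**The case against.** The strongest reply is that Table 1 is only a last resort. An AE end date inside the window, or a recorded action on study drug, can place the event first, and the version history for SAP 3.2 records an update to how the period is determined. This stands as a limit. A reader might infer that every January AE after a December last dose is counted as Post-treatment. The documents support that only for AEs that nothing else can date.

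A second reply is that 50% estimates nothing in the trial. This is also fair: it averages shares from 3% to 97% and assumes equal weights. Collection after day 30 narrows ("Beyond these 30 days, any serious adverse events that are suspected to be related to the study drug will also be collected"), so recorded January AEs may lie inside the window more often than equal weights suggest. The documents do not allow that to be quantified.

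A third reply is that the incidence may not move. Patients are counted once at worst grade (SAP 5.4.2.2), so a lost AE matters only if the patient has no other qualifying on-treatment event in that category. In addition, the AE overview in SAP 5.4.2.1 has rows for suspected AEs and SAEs that carry no explicit treatment-emergent restriction, although protocol 10.5.3.2 is stricter. Both points stand, so 1.7 points is a ceiling.

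A reader might also infer a second error from overlapping rows. If first and last dose fall in one calendar year, an AE in last-dose month + 3 or later of that year meets both a Treatment period row and a Post-treatment row, and no precedence is stated. However, the smallest gap there is 60 days (31 January to 1 April, non-leap year). The known month and year already prove that the AE is outside the window, so the SAP's lead-in settles it before Table 1 is used. The wording is untidy, but no AE is misplaced by it.

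**Conclusion.** The day-missing later-year row departs from the SAP's own 30-day window for January AEs after last doses on 2–31 December. It also departs from the table's handling of the same day arithmetic within a year. It runs against the SAP's inclusive approach elsewhere: a wholly missing onset date goes to Treatment period, and missing causality counts as suspected. The rule is wrong as written and should be corrected, because it feeds the primary endpoint.

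The practical effect is probably very small. The documents give no count of partly dated AEs around a year end, and the ceiling is 1.7 percentage points per affected patient.

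Two wider readings are not supported:

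- The year-only and month-missing blocks use the same later-year wording, but far fewer of their possible dates lie inside. For year-only AEs after a December last dose it is 465 of 31 × 365 = 11,315 pairs (4.1%). For month-missing AEs it is about 8% (465 of 5,577), even when the known day would fit the January window. Post-treatment is a defensible choice there.
- The rule for deaths in SAP 5.4.2.4.1 ("If only the day is missing, it is imputed with the 1st of the current month") differs from the 15th in protocol 14.1.36. That appendix describes itself as guidance (14.1.28), and the SAP may set its own rule and logged it in its version history. It is a choice, not a parallel error.

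**What to change.** For AEs with only the day missing, replace the rows by one rule:

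- Post-treatment only if the first day of the AE month is later than last dose + 30 days;
- Pre-treatment only if the last day of the AE month is before first dose;
- otherwise Treatment period.

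Keep the existing Table 1 note that an AE ending before first dose is pre-treatment. The Pre-treatment result is otherwise unchanged, since an AE month earlier than the first-dose month always ends before first dose. First dose cannot follow last dose, so no AE can meet both of the first two conditions. The rows therefore become mutually exclusive, which is tidying.

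**Cost.** SAP wording and minor programming, with no new data. Some of the January AEs added will truly lie outside the window (half of the pairs under equal weights), which is in line with the inclusive handling elsewhere. AEs in last-dose month + 2, which the present row would count as Treatment period, become Post-treatment except where the window can still reach them (30 or 31 January to early March in a non-leap year, the 3 pairs in 9,305). Nearly all of these are already settled by the known month and year. Any AE that leaves the summary tables stays in the listings with its period flagged.

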5.4.2.1 Overview of adverse events

The overview of adverse events included the number and percentage of patients with the following AE (reported by all grades and Grade 3/4, respectively):

- All death events
- Treatment-emergent deaths (all grades only reported)
- Treatment-emergent AE
- AE suspected to be related to the study drug
- Treatment-emergent SAE
- SAE suspected to be related to the study drug
- AE leading to discontinuation of medication
- AE leading to discontinuation of medication, suspected to be related to the study drug
- Other significant treatment-emergent AE (AE leading to interruption or change in dose or frequency of Afinitor, AE requiring additional treatment)

5.4.2.2 All treatment-emergent adverse events

The number and percentage of patients with treatment-emergent AE (including all grades and Grade 3/4) (regardless of study drug-related or not) were summarized by SOC (in descending order of incidence).

The number and percentage of patients with treatment-emergent AE (including all grades and Grade 3/4) (regardless of study drug-related or not) were summarized by PT (in descending order of incidence).

The number and percentage of patients with common treatment-emergent AE (incidence $\geq 5\%$) were summarized by PT (in descending order of incidence).

The number and percentage of patients with treatment-emergent AE (regardless of study drug-related or not) were summarized by PT (in descending order of incidence) and CTCAE grade (Grade 1, Grade 2, Grade 3, Grade 4, and Grade 3/4). A patient would be categorized and analyzed based on the most severe one if he/she experiences an AE of different severities for many times.

The number and percentage of patients with treatment-emergent AE suspected to be related to the study drug were summarized by PT (in descending order of incidence) and CTCAE grade (Grade 1, Grade 2, Grade 3, Grade 4, and Grade 3/4). A patient would be categorized and analyzed based on the most severe one if he/she experiences an AE of different severities for many times.

The number and percentage of patients with treatment-emergent AE (regardless of study drug-related or not) were summarized by SOC (in descending order of incidence) and CTCAE grade (Grade 3, Grade 4, and Grade 3/4). A patient would be categorized and analyzed based on the most severe one if he/she experiences an AE of different severities for many times.

The number and percentage of patients with common treatment-emergent AE (incidence $\geq 5\%$) (regardless of study drug-related or not) were summarized by PT (in descending order of incidence) and CTCAE grade (Grade 3, Grade 4, and Grade 3/4). A patient would be categorized and analyzed based on the most severe one if he/she experiences an AE of different severities for many times.

The number and percentage of patients with treatment-emergent AE suspected to be related to the study drug were summarized by PT (in descending order of incidence) and CTCAE grade (Grade 3, Grade 4, and Grade 3/4). A patient would be categorized and analyzed based on the most severe one if he/she experiences an AE of different severities for many times.

The number and percentage of patients with treatment-emergent AE (excluding SAE) (regardless of study drug-related or not) were summarized by SOC (in alphabetical order) and PT (in descending order of incidence).

The number and percentage of patients with treatment-emergent AE (regardless of study drug-related or not) were summarized by SOC (in alphabetical order), PT (in descending order of incidence), and CTCAE grade (all grades). A patient would be categorized and analyzed based on the most severe one if he/she experiences an AE of different severities for many times.

5.4.2.3 Adverse events of special interest

Adverse events of special interest in this study included: non-infectious pneumonitis, stomatitis/oral mucositis, hepatitis B virus reactivation and cardiac disease: heart failure; ejection fraction decreased.

For non-infectious pneumonitis, SMQ (standard MedDRA query) (broad) "interstitial lung disease" was used to help retrieve relevant adverse events in the database.

For stomatitis/oral mucositis, the following terms were used as preferred terms to identify adverse events in the database.

- Mucosal inflammation
- Lip ulceration
- Glossitis
- Gingival ulceration
- Gingival swelling
- Mucosal ulceration
- Tongue ulceration
- Gingival pain
- Glossodynia
- Stomatitis
- Mouth ulceration

- Aphthous ulcer

For hepatitis B virus reactivation, the following terms were used as preferred terms to identify adverse events in the database.

- Hepatitis viral test positive
- Hepatitis B
- Infection reactivation
- Hepatitis B antibody
- Hepatitis B surface antibody positive
- Hepatitis B virus test positive
- Viral hepatitis carrier

For cardiac diseases: heart failure and the ejection fraction decreased, SMQ (narrow) "cardiac failure" was used to help retrieve relevant adverse events in the database.

The number and percentage of patients with non-infectious pneumonitis were tabulated and summarized by:

- At least one non-infectious pneumonitis
- Non-infectious pneumonitis suspected to be related to the study drug
- At least one severe (Grade 3 or 4) non-infectious pneumonitis
- Severe (Grade 3 or 4) non-infectious pneumonitis suspected to be related to the study drug.

In addition, the following AE was individually tabulated and summarized by the number and percentage of patients:

- Non-infectious pneumonitis, regardless of study drug-related or not graded by CTCAE
- Non-infectious pneumonitis leading to discontinuation of treatment, interruption or change in dose or frequency of Afinitor, suspected to be related to the study drug

Non-infectious pneumonitis was tabulated by patient.

Similar methods were used for analysis of stomatitis/oral mucositis, hepatitis B virus reactivation and cardiac diseases: heart failure; ejection fraction decrease.

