6.3.2.1 Follow up on potential drug-induced liver injury (DILI) cases

Patients with transaminase increase combined with TBIL increase may be indicative of potential DILI, and should be considered as clinically important events.

The threshold for potential DILI may depend on the patient's baseline AST/ALT and TBIL value; patients meeting any of the following criteria will require further follow-up as outlined below:

- For patients with normal ALT and AST and TBIL value at baseline: AST or ALT $>$ 3.0 x ULN combined with TBIL $>$ 2.0 x ULN
- For patients with elevated AST or ALT or TBIL value at baseline: [AST or ALT $>$ 2 x baseline AND $>$ 3.0 x ULN] OR [AST or ALT $>$ 8.0 x ULN], combined with [TBIL $>$ 2 x baseline AND $>$ 2.0 x ULN]

Medical review needs to ensure that liver test elevations are not caused by cholestasis, defined as ALP elevation $>$ 2.0 x ULN with R value $<$ 2 in patients without bone metastasis, or elevation of ALP liver fraction in patients with bone metastasis.

Note: (The R value is calculated by dividing the ALT by the ALP, using multiples of the ULN for both values. It denotes whether the relative pattern of ALT and/or ALP elevation is due to cholestatic (R \leq 2), hepatocellular (R \geq 5), or mixed (R $>$ 2 and $<$ 5) liver injury).

In the absence of cholestasis, these patients should be immediately discontinued from study drug treatment, and repeat LFT testing as soon as possible, preferably within 48 hours from the awareness of the abnormal results. The evaluation should include laboratory tests, detailed history, physical assessment and the possibility of liver metastasis or new liver lesions, obstructions/compressions, etc.

1. Laboratory tests should include ALT, AST, albumin, creatine kinase, total bilirubin, direct and indirect bilirubin, GGT, prothrombin time (PT)/INR and alkaline phosphatase.
2. A detailed history, including relevant information, such as review of ethanol, concomitant medications, herbal remedies, supplement consumption, history of any pre-existing liver conditions or risk factors, should be collected.
3. Further testing for acute hepatitis A, B, C or E infection and liver imaging (e.g. biliary tract) may be warranted.
4. Obtain PK sample, as close as possible to last dose of study drug, if PK analysis is performed in the study.

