7.2.2.4.2 Liver function tests

Total bilirubin, AST, ALT, serum albumin and alkaline phosphatase will be measured.

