10.5.3.2 Adverse events (AEs)

Summary tables for adverse events (AEs) have to include only AEs that started or worsened during the on-treatment period, the ***treatment-emergent*** AEs. However, all safety data (including those from the pre and post-treatment periods) will be listed and those collected during the pre-treatment and post-treatment period are to be flagged.

The incidence of treatment-emergent adverse events (new or worsening from baseline) will be summarized by system organ class and or preferred term, severity (based on CTCAE grades), type of adverse event, relation to study treatment

Serious adverse events (SAE), non-serious adverse events and adverse events of special interest (AESI) during the on-treatment period will be tabulated

All death (on-treatment and post-treatment) will be summarized.

The adverse events of special interest (AESI) include the following categories

- Non-infectious pneumonitis
- Stomatitis/ oral mucositis
- Reactivation of hepatitis B virus
- Cardiac disorders: Cardiac failure; ejection fraction decreased

All AEs, deaths and serious adverse events (including those from the pre and post-treatment periods) will be listed and those collected during the pre-treatment and post-treatment period will be flagged

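### The SAP counts hepatitis B antibody and carrier findings as virus reactivation, with no scheduled baseline test and no stated case review

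*SAP*

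**What the plan says.** Protocol 8.1.3 and 10.5.3.2 name "Reactivation of hepatitis B virus" as one of four categories of AEs of special interest. Neither section gives a case definition.

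SAP 5.4.2.3 supplies the working rule: "For hepatitis B virus reactivation, the following terms were used as preferred terms to identify adverse events in the database". Seven terms follow, among them "Hepatitis B surface antibody positive", "Viral hepatitis carrier" and "Infection reactivation". On reporting, the same section says: "Similar methods were used for analysis of stomatitis/oral mucositis, hepatitis B virus reactivation and cardiac diseases". The model is the pneumonitis analysis, which gives counts and percentages of patients (all, drug-suspected, Grade 3 or 4) and a by-patient tabulation.

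The scheduled liver panel in protocol 7.2.2.4.2 is: "Total bilirubin, AST, ALT, serum albumin and alkaline phosphatase will be measured". The one mention of hepatitis testing is in the work-up of potential drug-induced liver injury (protocol 6.3.2.1): "Further testing for acute hepatitis A, B, C or E infection and liver imaging (e.g. biliary tract) may be warranted".

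**The concern.** Reactivation is a change from an earlier state. An antibody result or carrier status is a state, and so is a single positive test. A rule that identifies reactivation from such terms needs either a known baseline or a review of each record, and the plan states neither.

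The study was set up because the approval in China came without safety data in Chinese patients (protocol 2.1), and safety is its primary objective. The reported figure for this event will rest on very few patients, so one or two records of HBV status counted as reactivation could make up much or all of it.

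**Working it through.** The plan has no figure to reproduce. The sample size of about 60 is based on feasibility, and neither document gives an HBV prevalence or an expected case count. The check is a reading of the rule, followed by arithmetic for scale.

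**Step 1: what the seven terms denote.** The documents do not define them, so this is a plain reading of the wording.

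| Term in SAP 5.4.2.3 | Denotes |
|---|---|
| Hepatitis B surface antibody positive | antibody result |
| Hepatitis B antibody | antibody, type and result unspecified |
| Viral hepatitis carrier | carrier status |
| Hepatitis viral test positive | positive test, virus not named |
| Hepatitis B virus test positive | positive test |
| Hepatitis B | diagnosis |
| Infection reactivation | reactivation, virus not named |

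Three of seven are antibody or carrier findings, two are positive tests with no reference to an earlier state, and two are relevant clinical terms.

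**Step 2: is there a baseline?** The visit schedules (protocol Table 7-1, SAP Appendix 1) contain no HBV serology or DNA. HBV is absent from the eligibility criteria, the liver panel and the example laboratory tests in protocol 7.2.2.4.6. Other laboratory tests are marked as source-only in Table 7-1, so an HBV test done on clinical grounds would not by that route enter the database as a result.

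**Step 3: follow a status finding through the rules.**
- Known at consent: protocol 8.1.1 sends it to medical history. It is not counted.
- First found on treatment: it becomes an AE only if it causes signs or symptoms, is judged clinically significant, or requires therapy or a change in study medication (protocol 8.1.1). A positive test or carrier status found while raised liver tests are being worked up can meet this.
- Onset date: a date of first detection during treatment passes the treatment-emergent filter. If the onset date is wholly missing and other information does not resolve it, SAP Table 1 assigns the event to the treatment period. The note under that table moves an event to pre-treatment when it ended before the first dose, and a persisting status has no such end date.
- Causality: if missing or unknown, SAP 5.4.2 sets it to suspected related.
- Classification: no later step in SAP 5.4.2.3 asks whether the record shows a change.

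Followed as written, the rule reports such a patient as a reactivation case.

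**Step 4: scale at n = 60.** One extra case adds 1/60 = 1.67 percentage points. Exact (Clopper-Pearson) 95% limits are the 2.5% quantile of Beta(x, n − x + 1) and the 97.5% quantile of Beta(x + 1, n − x).

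| Cases x | x/60 | 95% CI |
|---|---|---|
| 1 | 1.67% | 0.04 to 8.94% |
| 2 | 3.33% | 0.41 to 11.53% |
| 3 | 5.00% | 1.04 to 13.92% |

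The false-case rate f per patient is not in the documents. With f as an assumption and patients independent, the chance of at least one false case is 1 − (1 − f)^60: 45% at f = 1%, 70% at 2% and 95% at 5%. With an assumed true rate of 1%, f = 2% and no true case missed, the apparent rate is 1 − 0.99 × 0.98 = 2.98%, and about 0.01/0.0298 = 34% of counted patients are true cases.

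**The case against.** The strongest reply is that safeguards elsewhere in the plan already do most of the work. Sites are told to record a diagnosis rather than a finding where possible (protocol 8.1.1 and 8.1.2), so a real event would most naturally appear under Hepatitis B, which is on the list. A bare immunity result would ordinarily not qualify as an AE. Status known at consent goes to medical history, and only treatment-emergent events are summarised. Hepatitis reactivation is on the targeted follow-up list in protocol 8.2.2. The by-patient tabulation lets a reader see which records were counted.

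Most of this stands, and it limits the error. It does not cover carrier or test-positive status first discovered on treatment and judged clinically significant. The SAP does not use the targeted follow-up information to classify cases. A listing allows a reader to notice a wrong case, but the published percentage still includes it.

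A reader might infer that the count does not measure reactivation at all. The documents do not support that, since two of the seven terms are relevant and the safeguards remove known pre-existing status. A reader might also infer that dividing by all patients is wrong. Protocol 10.1.2 and 10.5.3.1 require the Safety Set for safety analyses, and incidence among treated patients is a valid descriptive quantity.

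**Conclusion.** The rule in SAP 5.4.2.3 is wrong as written, though its reach is narrow. The count is a non-specific proxy for HBV reactivation, because three antibody or carrier terms and two bare positive-test terms can each make a case with no evidence of change. Each false case adds 1.7 percentage points at n = 60, so one false case beside one true case doubles the figure from 1.7% to 3.3%, although the intervals overlap widely.

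This rests on a plain reading of the term names, on the planned sample size, and on at least one status finding being discovered on treatment and entered as an AE. How often that happens cannot be derived from the documents, and neither can the net direction of error: without scheduled HBV testing, a silent true reactivation could also go unrecorded.

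The consequence should not be inflated. HBV reactivation is a special-interest category, but the endpoint lists in protocol Table 3-1 and SAP 2.3 name only non-infectious pneumonitis. Overall AE, drug-related AE, Grade 3/4 and SAE incidences do not depend on this term list. The change is still worth making because it is cheap and can alter a reported number.

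**What to change.** Amend SAP 5.4.2.3 as follows.

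1. State that the seven terms are a retrieval list only.
2. Take Hepatitis B antibody, Hepatitis B surface antibody positive and Viral hepatitis carrier out of the reactivation count. List them separately as HBV status findings.
3. Before database lock, have the remaining retrieved records medically reviewed against recorded medical history, targeted follow-up information, and the ALT, AST and bilirubin values already collected.
4. Show every retrieved record with its classification, including a category for baseline status unknown.
5. Keep the Safety Set as the denominator. As a supplement, state how many patients had HBV in their recorded medical history, noting that this covers known history only.

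No new patient procedure or data collection is needed. The cost is a short SAP revision and review of what should be a handful of records. The review adds some judgement, which the full listing makes visible.
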